10.2 Statistical analysis

Statistical analysis will by necessity (n=15) and nature (predictive modeling of response using patient-derived ex-vivo uVESSEL responses as predictors, among others) be exploratory and descriptive including qualitative comparison between responses based on PSMA-PET and RECIST 1.1 without a formal paired test of statistical significance.

Measures of patient response to anti-angiogenics via clinical endpoint such as response based on PSMA-PET (primary endpoint) and objective response based on RECIST 1.1 and histopathological endpoints (tumor vascular density, immunohistochemical staining for PSMA and neovascularization (CD30, CD34)) will be summarized with descriptive statistics (response rate and confidence interval), and changes in these endpoints, PSMA staining from baseline to end of treatment and follow-up) will also be summarized with descriptive statistics. Measures of tumor neovascularization via PSMA-based PET/CT imaging will be summarized with descriptive statistics over time and analyzed using generalized linear mixed-effects models for longitudinal measures. Qualitative ¹⁸F-DCFPyL PSMA PET/CT imaging will be recorded in a three-point scale, and statistical analysis will be performed with the equivocal score of 1 considered as positive or negative. Histopathological endpoints will be qualitatively graded by our study pathologist on a zero to four scale with four being the highest level of immunohistochemical staining or neovascularization.

Partial responses are likely from conventional clinical imaging in mRCC patients. Standard imaging techniques define responses to therapy based on size changes of target lesions using RECIST1.1. Metastatic tumors may respond to anti-angiogenic treatment but not change substantially in size (unlike cytotoxic therapies for which RECIST was designed). To address this limitation in current imaging, we combine standard imaging with functional imaging protocols to evaluate whether angiogenesis decreases in individual metastatic lesions regardless of changes in tumor size. PSMA PET signal is used as a surrogate for changes in tumor neovasculature. These functional imaging findings will be

confirmed pathologically by evaluating angiogenesis/ PSMA expression in tumor samples and patient models. Using this approach, we will evaluate functional anti-angiogenesis responses to therapies.

For the uVESSEL models (secondary objective 1), generalized linear mixed-effects models for longitudinal measures taken four times will be used for various endpoints with treatment (control plus four anti-angiogenics), dose (three levels each replicated three times), and plate (primary vs metastatic crossed by normal vs tumor) as the main factors. This will allow evaluation of the effects of treatment and dose and the differences between primary and metastatic samples and between normal and tumor vessels. We will also include these two models as the main factor in a combined generalized linear mixed-effects model, which will allow direct comparison of the biomimetic and the organotypic models.

Predictive modeling (secondary objective 2) will thus include the actual tumor size change (in a typical waterfall plot) and the dichotomy of disease control vs no disease control in the predictive model for tumor response in addition to the dichotomy of responders vs. non-responders in functional studies.

Due to limited sample size (n=15) and because not all patients are treated with the same anti-angiogenic therapy, further reducing the sample size for each anti-angiogenic therapy, one cannot expect the predictive analysis to give a clear discrimination between responders and non-responders to anti-angiogenic therapies. As an alternative, we will also use clustering analysis based on k-means or Gaussian mixture models which are less sensitive to small sample sizes as in Pak (2015).

Using the clinical, pathological and imaging endpoints as dependent variables, we will develop predictive models using responses to the uVESSEL model as independent predictor variables. More specifically, we will use the objective response as a dichotomous endpoint as a dependent variable in a logistic regression model with response to the uVESSEL model as an independent predictor. This approach is equivalent to linear discriminant analysis. Although we expect about 70% of eligible patients will receive pazopanib and the rest sunitinib, we can still use the objective response as the dependent variable in logistic regression as both pazopanib and sunitinib are expected to give a similar response rate of around 30% in this patient population. In addition each patient sample will be subject to both agents in the uVESSEL model and provide response to be used as predictors in logistic regression modeling.

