10.0 STATISTICAL CONSIDERATIONS

As noted in section 3.0, the primary objective is to evaluate response to anti-angiogenesis therapy using PSMA-based PET. Other endpoints such as qualitative objective response based on RECIST 1.1 and quantitative CT-based tumor size and SUV parameters will also be evaluated. The secondary objectives are 1) to measure therapy response of patient-derived uVESSEL models using multiple endpoints such as vessel sprouting, PSMA expression and cell death and 2) to evaluate the predictive power and validate the uVESSEL model for clinical outcomes.

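### Section 10.2 reads change in single lesions from PSMA PET signal without allowing for lesion size, so in small lesions that shrink, a fall in SUV partly restates the CT shrinkage

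*Combined protocol and SAP*

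**What the plan says.** Section 10.2 argues that RECIST 1.1 can miss an anti-angiogenic effect, since "Metastatic tumors may respond to anti-angiogenic treatment but not change substantially in size". Its answer is to add functional imaging and "evaluate whether angiogenesis decreases in individual metastatic lesions regardless of changes in tumor size". The link from image to biology is stated directly: "PSMA PET signal is used as a surrogate for changes in tumor neovasculature".

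Two kinds of PET result are planned. One is visual: section 10.2 says the qualitative "imaging will be recorded in a three-point scale". The other is numerical: section 10.0 says that "quantitative CT-based tumor size and SUV parameters will also be evaluated", and section 10.2 says that PET measures of neovascularization are summarized over time and "analyzed using generalized linear mixed-effects models for longitudinal measures".

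Shrinking lesions are expected. Section 10.2 says "Partial responses are likely from conventional clinical imaging in mRCC patients", and later that "both pazopanib and sunitinib are expected to give a similar response rate of around 30% in this patient population".

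The documents do not state the SUV metric (maximum, peak or mean), the scanner resolution, a minimum lesion diameter for PET analysis, a partial-volume correction, a lesion-size covariate, or a split of lesions by size change. Section 5.0 gives the CT part of the PET/CT two uses only, attenuation correction and anatomic registration.

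**The concern.** A PET scanner blurs the image. In a lesion only a few times wider than the blur, activity spills out and measured SUV lies below true uptake; the smaller the lesion, the larger the shortfall. A small metastasis that shrinks therefore shows a lower SUV at the second scan even if its PSMA density has not changed. A small lesion that grows shows a higher SUV, which can cover a real fall.

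The stated purpose of the PET arm is information beyond size. If SUV change in small lesions is reported as neovascular change without regard to diameter, part of an apparent anti-angiogenic effect may be CT shrinkage seen a second time. Under section 3.2.2, PET-based response is also the dependent variable for validating the uVESSEL model, so a responder call that relied on SUV would carry the same component into that analysis.

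**Working it through.** **The plan's own figure.** The only number given for SUV is the standard error in section 10.1, 0.258 times the standard deviation. It reproduces: 1/√15 = 0.258. It describes sampling error and says nothing about a shift that goes in one direction.

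**Inputs.** None of the following is in the documents; all are assumptions. The lesion is a uniform sphere with constant true uptake. The scanner has a Gaussian point spread of 5-7 mm full width at half maximum (FWHM). Diameter falls by 30%. Background is either zero or one fifth of lesion uptake. SUV is the noise-free central (peak) value.

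**Formulas.** With σ = FWHM/2.355 and z = radius/σ, the recovered fraction at the centre is RC = erf(z/√2) − √(2/π)·z·exp(−z²/2). With uptake T times background, the measured value relative to true uptake is M = (RC·(T−1)+1)/T; with zero background, M = RC. Spurious loss = 1 − M(after)/M(before).

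**Worked case, 10 to 7 mm at 6 mm FWHM.** σ = 6/2.355 = 2.548 mm.
- Before: z = 5/2.548 = 1.962, RC = 0.722.
- After: z = 3.5/2.548 = 1.374, RC = 0.404.
- Zero background: loss = 1 − 0.404/0.722 = 44%.
- T = 5: M(before) = (4×0.722+1)/5 = 0.778, M(after) = (4×0.404+1)/5 = 0.523, loss = 33%.

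**Range over 5-7 mm FWHM, true uptake unchanged, peak SUV:**

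| Diameter before to after | Loss, zero background | Loss, uptake 5× background |
|---|---|---|
| 10 to 7 mm | 35-50% | 27-35% |
| 15 to 10.5 mm | 10-31% | 8-24% |
| 20 to 14 mm | 1-13% | 1-10% |
| 30 to 21 mm | under 1% | under 1% |
| any size, unchanged | 0% | 0% |

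**Smaller shrinkage.** With a 10% diameter decrease the losses (zero / 5× background) are 9-16% / 7-12% at 10 mm, 1-7% / 1-6% at 15 mm, and under 2% at 20 mm.

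**Growth.** From 10.5 to 15 mm at 6 mm FWHM and zero background, RC goes from 0.764 to 0.966. Measured SUV rises by 0.966/0.764 − 1 = 26% at constant uptake, so a true fall of 1 − 0.764/0.966 = 21% would leave the reading unchanged.

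**The metric matters.** If SUV is the mean over the whole lesion, 30 to 21 mm still gives 8.5-12.5% (zero background) or 6.5-9.4% (5×), because the blurred rim is always inside the region.

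**The case against.** The strongest defence is that the size-independence sentence answers the one before it, about lesions that respond without changing much in size. In such lesions the artefact is nil. The sentence also states an aim; it does not assert that measured SUV is numerically independent of diameter. This stands, and it means the main argument for PET in section 10.2 is untouched.

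Several stronger readings are tempting, and the documents do not support them.
- A reader might infer that every lesion enters the PET analysis whatever its size. The documents are silent on lesion selection. Section 3.1 speaks of index lesions at progression and section 5.0 of remaining measurable disease.
- A reader might infer that agreement between PET and RECIST 1.1 is built in. The planned comparison is qualitative, with no paired test, and section 10.1 frames PET response as qualitative. A visual score is touched only through apparent contrast, and no SUV threshold for response is given. The overlap is shown for SUV change only.
- A reader might take the zero-background losses as the expected size. They are the worst case in the model; at five times background they are lower.
- A reader might infer that any lesion shrinking on CT will show a material SUV fall. At 30 mm the peak falls by under 1%.

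It can also be said that the analysis is declared exploratory with 15 patients, that CT size is reported beside SUV, and that pathology will confirm the imaging. The first two limit the consequences, but a one-directional shift remains in a descriptive table, and reporting size and SUV side by side does not separate them. On the third, section 10.2 does mention change in PSMA staining to end of treatment, but the only tissue entry in the Study Procedures Table is tied to surgery, so no on-treatment check of each lesion is scheduled.

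**Conclusion.** The point holds for small lesions whose diameter changes. As written, section 10.2 gives no means of separating lower PSMA uptake from smaller size in those lesions. Under the stated assumptions, a 30% shrinkage alone takes roughly a quarter to a half off peak SUV at 10 mm, 8-31% at 15 mm, 1-13% at 20 mm, and almost nothing at 30 mm.

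The effect in this trial cannot be fixed from the documents, because lesion sizes, resolution, background and SUV metric are all unstated; it may be small or material. It concerns SUV parameters first and the three-point read only weakly. No error rate, decision rule or sample size depends on it. This is an inexpensive improvement to the analysis text and does not threaten the design.

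**What to change.** In section 10.2:
- Report lesion SUV change separately for lesions whose CT diameter was stable, fell or rose, and by baseline diameter. Define the margin for stable in advance and keep it narrow for small lesions: a 10% decrease at 10 mm still gives 7-16%. Name the SUV metric in the same place.
- Stratify on baseline diameter only. Requiring a minimum size at both scans would select on post-treatment size, drop shrinking lesions, and protect only peak SUV.
- Keep growing lesions apart from stable ones, since rising recovery can mask a true fall.
- Add CT diameter as a time-varying covariate in the planned mixed model, fitted with lesions nested in patients, as a sensitivity analysis. It should stay a sensitivity analysis because shrinkage may itself follow from treatment, so adjustment can remove real effect.
- Rest any statement that angiogenesis fell independently of size on the size-stable lesions, and say that it applies to them.

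The cost is a little more analysis and fewer lesions per stratum, which with 15 patients means descriptive results only. The CT measurements come from the standard-of-care imaging already planned around the PET scans, so no new data are needed.

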3.2.2 Evaluate the predictive power and validate the uVESSEL model

While a number of novel biomimetic approaches show promise in their ability to recapitulate physiologically relevant behavior, clinical validation is needed to determine if such approaches are predictive. Using the clinical, pathological and imaging endpoints under 3.1, we will develop predictive models using responses to uVESSEL model above. More specifically we will use the objective response (dichotomous endpoint of yes or no) measured using PSMA-based PET/CT as a dependent variable in a logistic regression model with response to uVESSEL model from above as an independent predictor to segregate uVESSEL responses into two groups corresponding to responders and non-responders to anti-angiogenic therapies.

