3.2.3 Evaluate the predictive power and validate in-vitro immune therapy models

At the moment we are expanding our uVESSEL patient-specific organotypic models (Fig. 2) to contain more cell types from the tumor microenvironment (cancer epithelial, endothelial, immune, stromal) in similar proportions as found *in vivo*.

Patient tissue can be disaggregated, specific cell types isolated and placed in the uVESSEL model (Bischel 2014) (Jimenez-Torres et al 2019). Tumor spheroids can be created from a mixture of tumor epithelial cells and immune cells, to mimic tumor-infiltrating leukocytes, embedded in a hydrogel matrix (Sung 2014). Tumor spheroids model solid tumors and replicate the hypoxia and

[figure not shown]

Fig. 2. A) Left: model scheme showing a tumor spheroid flanked by 2 endothelial lumens. Right: a 4-microdevice array. Confocal images of B) a tumor spheroid (blue) and immune cells (green). C) tumor organoid (green) with hypoxic core (red). D) lateral endothelial lumen.

nutrient starvation observed *in vivo* in RCC (Fig. 2). Hypoxia influences the microenvironment by significantly suppressing the anti-tumor response by increasing regulatory and immunosuppressive immune cell phenotypes and reducing cytotoxic lymphocyte functions (Noman 2015). Likewise, the uVESSEL model allows for the creation of lumen structures within a hydrogel matrix that can be lined with endothelial cells to form microvessel structures, mimicking the highly vascularized nature of RCC (Jimenez-Torres 2019). Thus, we can create a carefully controlled model tumor microenvironment made entirely of primary cells all from the same patient (Fig. 2) that can be treated with various immune checkpoint inhibitors, TKI's or combinations thereof with readouts examining tumor growth, immune cell phenotype and function and angiogenesis. Our functional endpoints include spheroid size variation/viability, as well as the angiogenic sprouting endpoint already developed for TKI predictive value. Both outputs can be expressed as a dichotomous endpoint of responders/non-responders for the validation of uVESSEL performance with patient response as observed in PET/CT.

4.0 RESEARCH DESIGN AND METHODS:

Study Design: This study is designed as a single cohort study without randomization or stratification.

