10.1 Sample size justification

A total of 15 patients will be recruited into this clinical study. This is based on the feasibility and availability of suitable patients over the funding period with approximately five patients per year. With 15 patients, the width of a 95% confidence interval for the probability of qualitative response based on PSMA-PET and objective response based on RECIST 1.1 will be less than 0.253 and the mean of quantitative endpoints such as CT-based tumor size and SUV parameters will have standard error that is 0.258 times the sample standard deviation.

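### The uVESSEL logistic model is not equivalent to linear discriminant analysis, and with about 4.5 expected responders it may have no finite estimate, more often the better the assay discriminates

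*Combined protocol and SAP*

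**What the plan says.** Section 10.2 of the combined protocol and SAP specifies the model for secondary objective 2: "we will use the objective response as a dichotomous endpoint as a dependent variable in a logistic regression model", with uVESSEL response as the independent predictor. The next sentence is "This approach is equivalent to linear discriminant analysis", with no condition attached. No penalty, exact method or rule for separated data is named.

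The inputs that fix the amount of information are in the same part of the plan:

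- Sample size (10.1): "A total of 15 patients will be recruited into this clinical study".
- Response rate (10.2): "both pazopanib and sunitinib are expected to give a similar response rate of around 30% in this patient population".
- Predictors (10.2): "each patient sample will be subject to both agents in the uVESSEL model and provide response to be used as predictors". So one or two assay readouts may enter the model.

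Section 3.2.2 defines the outcome by PET: "we will use the objective response (dichotomous endpoint of yes or no) measured using PSMA-based PET/CT as a dependent variable in a logistic regression model". No expected rate is given for that outcome. Section 3.2.3, on the immune-therapy models, allows a yes/no readout: "Both outputs can be expressed as a dichotomous endpoint of responders/non-responders".

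Section 10.2 also calls the analysis exploratory and descriptive, warns that 15 patients cannot be expected to give clear discrimination, and adds k-means or Gaussian mixture clustering as an alternative.

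**The concern.** Linear discriminant analysis estimates group means and a pooled covariance. Logistic regression maximises the conditional likelihood of the outcome given the predictors. Under normal predictors with equal covariance both target the same linear log-odds, but in a sample they give different coefficients, and they behave differently at the extremes. When some linear combination of predictors divides responders from non-responders, or when a 2x2 table has an empty cell, no finite logistic maximum-likelihood estimate exists. The discriminant function can still be computed when a continuous predictor separates the groups.

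With so few responders this is a practical risk, and it grows with assay accuracy. If it happens, the planned model gives no usable slope or odds ratio, and the analyst must choose a rescue method after seeing the data. A reader who relies on the equivalence sentence would not expect the problem.

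**Working it through.** The plan states no responder count, power or precision for the prediction model, so there is no figure of its own to reproduce.

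**Inputs from the documents.** n = 15 (10.1); response rate about 0.30 (10.2); one or two predictors (10.2).

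**Assumed inputs.** Assay accuracy, normality of continuous readouts, and a correlation of 0.5 between the two agents' readouts. The documents give none of these, so ranges are shown.

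**Expected responders.** 15 x 0.30 = 4.5. The binomial probability of 2 or fewer is 12.7%, and of none is 0.7^15 = 0.5%. Responders per predictor: 4.5 with one predictor, 4.5/2 = 2.25 with two.

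**One continuous predictor.** Equal-variance normal readouts, mean shift = sqrt(2) x probit(AUC), which is 1.19, 1.81 and 2.33 at AUC 0.80, 0.90 and 0.95. Simulated share of trials with no overlap between responders and non-responders:

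| AUC | No finite estimate |
|---|---|
| 0.70 | about 2% |
| 0.80 | about 7% |
| 0.90 | 20-21% |
| 0.95 | 39-40% |

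**Two continuous predictors** (both agents, correlation 0.5, each at the stated AUC; separability checked by linear programming): about 18-20% at AUC 0.80 and 46-48% at 0.90. The ranges reflect simulation error.

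**Dichotomised predictor.** With r responders, k = 15 - r non-responders and sensitivity = specificity = s, the chance of an empty cell is

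1 - [1 - s^r - (1-s)^r] x [1 - s^k - (1-s)^k].

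For example, s = 0.8, r = 4, k = 11 gives 1 - 0.5888 x 0.9141 = 0.462. Averaging over r ~ Binomial(15, 0.30), and counting trials with only one outcome as failures, gives:

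| s | No finite odds ratio |
|---|---|
| 0.7 | 29% |
| 0.8 | 48% |
| 0.9 | 77% |

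**Sensitivity to the response rate.** The 30% figure belongs to objective response on two named agents, and 3.2.2 gives no PSMA-PET rate. Over an assumed 20-50%, the dichotomised figure at s = 0.8 runs from 62% to 38%.

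**The equivalence claim on identical data** (one continuous predictor). Where the logistic slope was finite, it differed from the discriminant slope by a median of 17%, 21% and 24% at AUC 0.80, 0.90 and 0.95. Where the logistic slope was infinite, the discriminant slope was finite, with a median of 3.1 to 3.6.

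**The case against.** Much of the case on the other side stands.

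- *The dichotomised readout is not the main case.* It comes from 3.2.3, which is a different objective, and it is optional there. Section 3.2.2 uses the logistic model to divide uVESSEL responses into two groups, which suggests an undichotomised input. A reader might take 29-77% as the headline risk; the documents do not support that. For one continuous readout of moderate accuracy the risk is only 2-7%.
- *Four predictors.* A reader might infer a joint fit with one predictor per drug. Section 10.2 speaks of one predictor and then of both agents, so two is the most it supports.
- *The objective does not rest on this model alone.* A reader might infer that no other analysis serves secondary objective 2. Section 10.2 also plans to use actual tumor size change, disease control versus none, and clustering.
- *A good assay would not necessarily look like a failure.* The plan promises no odds ratio, Wald interval or test here. Perfect classification would be visible as such. With one continuous predictor and the same slope sign, both methods rank patients identically and give the same AUC. Complete separation by a dichotomised readout is much rarer than an empty cell: about 0.8^15 = 3.5% at s = 0.8 and 0.9^15 = 21% at s = 0.9.

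What does not stand is that the plan's caveats already cover the matter. The warning in 10.2 concerns too little discrimination, whereas separation arises when discrimination is good. Clustering is unsupervised and supplies no coefficient or predicted probability of response. The exploratory label lowers the stakes but does not make the equivalence sentence true.

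**Conclusion.** The equivalence sentence is wrong as a statement about estimation. The plain logistic model carries a real risk of having no finite estimate. That risk is small for one continuous readout of moderate accuracy, about 20-40% for one excellent readout (AUC 0.90-0.95), just under half for two readouts at AUC 0.90, and larger still if an accurate readout is dichotomised. These sizes rest on assumed accuracy, normality and correlation, and on a 30% rate that the plan does not give for the PSMA-PET outcome. Reading the logistic model as unpenalised is an inference from the plan's silence, though the natural one.

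Severity is moderate to minor. A reader might infer that this must be settled before the trial can proceed. The documents do not support that, because the model is an exploratory secondary analysis and neither the primary endpoint nor the sample size depends on it.

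**What to change.** In section 10.2:

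1. Delete the sentence on linear discriminant analysis.
2. State that the dichotomous-response model will be fitted by Firth penalised logistic regression with profile penalised-likelihood intervals, or by exact logistic regression.
3. If uVESSEL response is dichotomised, also report the 2x2 table with exact intervals for sensitivity and specificity.

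The plan need not drop the joint use of both agents' readouts under the Firth option.

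As a check (n = 15, 30% response, one continuous predictor), Firth regression converged to a finite slope in at least 99.97% of simulated data sets.

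The cost is wording in the plan, with no added patients, visits or data, and shrinkage toward no effect. Median Firth slopes were 1.05, 1.51 and 1.72 against assumed true values of 1.19, 1.81 and 2.33 at AUC 0.80, 0.90 and 0.95. That is 1 - 1.05/1.19 = 12%, 1 - 1.51/1.81 = 17% and 1 - 1.72/2.33 = 26% too low. The shrinkage is largest where the assay is best, and the plan should say so when the estimates are interpreted.

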3.2.1 Measure therapy response of patient specific uVESSEL model

Patient-derived uVESSEL models (from primary & metastatic sites) and incorporating patient-derived immune cells will be tested for response to anti-angiogenic therapies including pazopanib, sunitinib, cabozantinib, and axitinib. Response will be quantified via multiple endpoints, e.g. vessel sprouting, PSMA expression, cell death.

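### Section 10.2 rests one pooled logistic model on a pazopanib/sunitinib mix that other sections do not share; it does not tie predictor or outcome to the drug received, and states no guard against optimism

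*Combined protocol and SAP*

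**What the plan says.** Section 10.2 plans a logistic regression of objective response (yes/no) on uVESSEL response. The reason for pooling all patients is: "Although we expect about 70% of eligible patients will receive pazopanib and the rest sunitinib, we can still use the objective response". The text adds that both drugs should give a response rate of about 30%. The predictors follow: "each patient sample will be subject to both agents in the uVESSEL model and provide response to be used as predictors". Of the logistic approach it says: "This approach is equivalent to linear discriminant analysis".

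The assay itself covers more drugs. In Section 3.2.1 the models "will be tested for response to anti-angiogenic therapies including pazopanib, sunitinib, cabozantinib, and axitinib", and the Section 10.2 assay model has "treatment (control plus four anti-angiogenics" as its treatment levels.

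The plan is candid about its limits. Section 10.2 calls the analysis exploratory and descriptive. It says of 15 patients on mixed agents that "one cannot expect the predictive analysis to give a clear discrimination between responders and non-responders", and it adds k-means or Gaussian-mixture clustering as an alternative.

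**The concern.** The uVESSEL prediction objective carries the claim in the trial's title. Its model needs three things settled before outcomes are read: which patients enter, which assay result belongs to each patient, and which clinical response is predicted. The pooling argument covers patients on two drugs only, and the predictors named are those same two drugs. If patients receive something else, two competent analysts could give the same patient different predictors and a different outcome, and both could cite the plan.

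The sample is also very small and the assay offers many readouts. Performance taken from the data used for fitting could look respectable for an assay that predicts nothing.

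**Working it through.** **1. The mix implied by Section 10.2.** Inputs: n = 15 (Section 10.1); about 70% on one drug and the rest on the other; about 30% response on each (Section 10.2).
- Pazopanib: 0.70 × 15 = 10.5 patients. Sunitinib: 0.30 × 15 = 4.5. The shares sum to 100%, which leaves no room for other regimens.
- Expected responders: 0.30 × 15 = 4.5 (0.30 × 10.5 = 3.15 plus 0.30 × 4.5 = 1.35).

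**2. The mix elsewhere.**
- Section 2.0, paragraph on clinical options: pazopanib and sunitinib are first-line; axitinib and cabozantinib come second. This agrees with Section 10.2.
- Section 2.0, paragraph on immunotherapy: a combination with no anti-angiogenic is called the preferred first-line standard.
- Sections 3.1 and 5.0: first-line therapy may be immune-based. PET3A and PET3B exist for patients whose first line had no anti-angiogenic and whose next line does.
- Section 5.0: any of four anti-angiogenic agents, at the physician's preference. Patients with locally advanced disease have no PET2A until metastases are found.
- Section 4.0: eligibility requires only that anti-angiogenic treatment be possible.

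**3. Predictor.** For a patient on pazopanib or sunitinib, the two named predictors include the drug received and one that was not. For a patient on cabozantinib or axitinib, neither is the drug received, although that drug is also assayed.

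**4. Outcome.** Section 3.2.2 defines objective response by PSMA-PET. Section 10.1 and the opening of 10.2 attach the term to RECIST 1.1. The logistic paragraph of 10.2 attaches it to neither. No section names the scan pair for this model. After immune-only first-line therapy, PET2A to PET2B does not span anti-angiogenic treatment; PET3A to PET3B does.

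**5. Equivalence with discriminant analysis.** Logistic regression maximises the likelihood of response given the predictors. Linear discriminant analysis estimates group means and a common covariance under normality. Both give a linear rule, but the estimates differ. If the responders separate perfectly, logistic coefficients diverge and discriminant coefficients do not.

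**6. Optimism.** The plan gives no performance figure to reproduce, so this is an illustration. Assumptions: 15 patients, 4 or 5 responders (around the 4.5 above), independent standard normal predictors unrelated to response, a logistic fit, and the AUC computed on the same data. The true AUC is 0.50. Results over 4,000 simulated datasets per case, with the range over repeated runs where they differed:

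| Predictors | Mean AUC on fitting data | AUC at least 0.8 |
|---|---|---|
| 1 | about 0.63 | about 7–8% |
| 2 (one readout for each of the two drugs) | 0.70–0.72 | about 19–23% |

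The 30% is given for unlabelled objective response on two drugs, and PSMA-PET response may differ.

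**7. Responders available.** With a binomial count at 30%, the chance of at most 2 responders is 0.13 at n = 15, 0.25 at n = 12 and 0.38 at n = 10. The documents do not give the share of patients without an anti-angiogenic. Assumed shares of 0, 25, 50 and 75% leave 15, 11.25, 7.5 and 3.75 patients, and 4.5, 3.4, 2.25 and 1.1 expected responders.

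**The case against.** The best defence is that this is a secondary, exploratory analysis whose authors already say it will not discriminate clearly, and who add clustering for that reason. That stands, and it lowers the severity. It does not define the predictor or the outcome, and clustering assay responses does not correct a fitted model's apparent performance.

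Several stronger readings are tempting, and the documents do not support them.
- *The whole protocol contradicts the 70/30 mix.* It does not. The treatment overview in Section 2.0 agrees with it, and some other sections only permit other therapy. The direct conflict is with the immunotherapy paragraph of 2.0 and the four-agent statement in 5.0.
- *The plan uses the wrong scan.* It does not say so. Section 3.2.2 aims at responders to anti-angiogenic therapy, which implies the pair around that line. What is missing is the rule.
- *All four agents enter the model together.* Four noise predictors would give a mean AUC of about 0.80 to 0.83 on the fitting data, but no section describes that model. The text supports one predictor, or two.
- *The assay's many readouts will be searched.* Section 3.2.1 says "Response will be quantified via multiple endpoints, e.g. vessel sprouting, PSMA expression, cell death", and Section 10.2 adds three doses, four plate types and "longitudinal measures taken four times will be used for various endpoints". That is 3 × 3 × 4 × 4 = 144 candidates per agent, but no screening of them is stated. The count shows why one should be named in advance, not that selection will occur.

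It is also fair to say that the plan names no AUC. The figures above are conditional on someone reporting one.

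**Conclusion.** The point holds as a gap in specification, with one false technical statement (the discriminant-analysis equivalence). The pooling argument does not cover patients on immune-only first-line therapy, cabozantinib or axitinib. The named predictors omit the drug received for the last two groups. The outcome's modality and scan pair are not fixed, and no protection against optimism is stated.

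No size can be put on the mismatch, because the documents do not say how many patients will fall outside the assumed mix. The size of the optimism is that of the table above and rests on 4 or 5 responders of 15 and on an AUC being computed from the fitting data. Severity is minor to moderate: the primary endpoint is untouched and the objective is exploratory.

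**What to change.** Reconcile the expected treatment mix in 10.2 with Sections 2.0 (both paragraphs), 3.1, 4.0 and 5.0. Replace the 70/30 sentence and the sentence on predictors from two agents with:

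> For secondary objective 2, the outcome is PSMA-PET response over the scan pair spanning the first line that contains an anti-angiogenic: PET2A–2B, or PET3A–3B if first-line therapy was immune-only. RECIST 1.1 response, tumour-size change and disease control over the same interval are separate analyses. Patients who never receive an anti-angiogenic are not in this model. The predictor is one uVESSEL readout for the agent received, as change from that patient's control, standardised within agent across all patient samples. The readout, its direction and the PSMA-PET responder definition are fixed before outcomes are read. Any performance figure from a fitted model is reported with internal validation, not from the fitting data alone. Individual data are shown with agent, line of therapy and combination flagged.

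Conform the logistic sentences in 3.2.2 and 10.2, keep the clustering as a supporting analysis, delete the discriminant-analysis sentence, and describe the result as exploratory, as 10.2 already does.

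Standardising within agent matters. Suppose two agents are used equally, with response rates of 30% and 60%, an assay shift of 1 to 2 SD between them, and no prediction within either (all assumed). Ranking raw readouts on one scale then gives a mean AUC of 0.58 to 0.63. Standardising is feasible because samples are assayed with all four agents.

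The cost is SAP wording and modest programming. Both scan pairs are already scheduled and all four agents already assayed. The downsides are fewer patients in the model and an imprecise estimate. Agents and lines stay pooled, so differences in response rate between agents are displayed but not removed.
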